7 ADVERSE EVENTS

An Adverse Event [AE] is defined as any new untoward medical occurrence or worsening of a pre-existing medical condition in a patient or clinical investigation subject administered an investigational (medicinal) product and that does not necessarily have a causal relationship with this treatment. An AE can therefore be any unfavorable and unintended sign (including an abnormal laboratory finding, for example), symptom, or disease temporally associated with the use of investigational product, whether or not considered related to the investigational product.

The causal relationship to study drug is determined by a physician and should be used to assess all adverse events (AEs). The causal relationship can be one of the following:

Related: There is a reasonable causal relationship between study drug administration and the AE.

Not related: There is not a reasonable causal relationship between study drug administration and the AE.

The term “reasonable causal relationship” means there is evidence to suggest a causal relationship.

Adverse events can be spontaneously reported or elicited during open-ended questioning, examination, or evaluation of a subject. (In order to prevent reporting bias, subjects should not be questioned regarding the specific occurrence of one or more adverse events).

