In the hospital, bleeding will be assessed daily by monitoring hemoglobin and the need for transfusions. After discharge and until the patient's 30-day post-operative evaluation, we will monitor for readmissions related to bleeding, indicated by the need for transfusion of at least two units of blood products. Any patient phone calls that already occur as part of routine post-operative care will continue; however, there are no additional post-discharge phone calls to the patient related to this study.

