6 STUDY ASSESSMENTS AND PROCEDURES

6.1 Time and Events Schedule

If a subject chooses to be removed from the study, withdraws informed consent, or if therapy must be stopped in the interest of the patient's safety, data collected to that point of the study will be collected for intent-to-treat analysis. We will document the reason for a patient's early withdrawal from the study, or the discontinuation of treatment for a patient by the patient's physician or study coordinator.

After the 30-day post-operative physician examination, there will be no further patient assessments. Analysis of all outcomes will be done by EMR analysis, except for treatment compliance as noted above.

Time and Events Schedule for Protocol: CV185-505

Procedure	Prior to Surgery (day of surgery, or <30 days prior)	After Diagnosis of AFib	Upon Hospital Discharge	At Each Anticoagulation Clinic Visit (warfarin)	At 30-Day Post-Operative Examination	After 30-Day Post-Operative Examination
Eligibility Assessments						
Informed Consent		X				
Medical History		X				
Inclusion/Exclusion Criteria		X				
Clinical Drug Supplies						
Randomize		X				
Dispense Study Treatment			X			
Patient Medication Consultation			X			
Safety Assessments						
Pregnancy Test for WOCBP	X					
Renal Function Test	X	X				
Hepatic Function Test		X				
INR measurement	X	X		X		
Monitoring for Bleeding Events			X	X	X	
Monitoring for Thrombotic Events			X	X	X	
Efficacy Assessments						
Measure Apixaban Adherence					X	
EMR Analysis of All Other Outcomes						X
Outcomes Statistical Analysis						X

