6.3 Safety Assessments

1) Major bleeding, as defined by the International Society on Thrombosis and Haemostasis based on the following criterion:

- a. Fatal bleeding, and/or
- b. Symptomatic bleeding that occurs in a critical area or organ, such as intracranial, intraspinal, intraocular, retroperitoneal, pericardial, in a non-operated joint, or intramuscular with compartment syndrome, assessed in consultation with the surgeon, and/or
- c. Extrasurgical site bleeding causing a fall in hemoglobin level of 20 g/L (2g/dL) or more, or leading to transfusion of two or more units of whole blood or red cells within 24-48 hours of the bleeding and/or
- d. Surgical site bleeding that requires a second intervention – open, arthroscopic, endovascular- or a hemarthrosis of sufficient size as to interfere with rehabilitation by delaying mobilization or delayed wound healing, resulting in prolonged hospitalization or a deep wound infection, and/or
- e. Unexpected surgical site bleeding, prolonged and/or sufficiently large to cause hemodynamic instability, as assessed by the surgeon, with a fall in hemoglobin of at least 20 g/L (2g/dL) or transfusion of two or more units of whole blood or red cells within 24 hours of the bleeding.³

2) Clinical relevant non-major bleed, defined as any notable bleeding not classified as major.

3) Pregnancy tests will be performed pre-operatively on the day of surgery for all WOCBP, via urine hCG screening.

4) A baseline renal function panel will be obtained either pre-operatively or within 30 days of surgery. The renal function panel includes: glucose, BUN, creatinine, BUN/creatinine ratio, sodium, potassium, bicarbonate, chloride, calcium, phosphorus, albumin, and anion gap.

5) The hepatic function test panel will be ordered before initiating warfarin (if a recent baseline is not available). This panel includes: total protein, albumin, alk phos, AST, ALT, total bilirubin, direct bilirubin, and indirect bilirubin.

6) INR will be checked before surgery to ensure the patient's INR is within normal limits in preparation for their surgery, regardless of whether they were previously on warfarin, and again upon initiation of warfarin therapy. INR will be checked daily in the hospital, and at each visit to the anticoagulation clinic. These visits are usually scheduled within three days of discharge from the hospital, then twice weekly until the INR is therapeutic, then weekly for the duration of the study.

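### Section 7 discourages asking about specific adverse events without exempting the endpoints; with EMR-only outcomes and a two-unit readmission rule, day-30 event rates could be biased low, most clearly non-major bleeding

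*Combined protocol and SAP*

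**What the plan says.** Section 7 sets the rule for eliciting adverse events. It first lists the permitted routes: "Adverse events can be spontaneously reported or elicited during open-ended questioning, examination, or evaluation of a subject". It then adds in parentheses, to guard against reporting bias, that "subjects should not be questioned regarding the specific occurrence of one or more adverse events". No endpoint is exempted.

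The schedule in section 6.1 has rows for "Monitoring for Bleeding Events" and "Monitoring for Thrombotic Events". Both are ticked at hospital discharge, at each anticoagulation clinic visit (a column labelled warfarin) and at the 30-day examination. The text above the schedule says: "Analysis of all outcomes will be done by EMR analysis, except for treatment compliance as noted above".

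Section 4.1 says that after discharge "we will monitor for readmissions related to bleeding, indicated by the need for transfusion of at least two units of blood products". The synopsis (Data Analysis Plan) has a matching rule. Section 4.1 keeps routine post-operative calls but says "there are no additional post-discharge phone calls to the patient related to this study".

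The endpoints are wider than that rule. Section 2.1 follows major and minor bleeding to postoperative day 30. Section 6.3 lists "Clinical relevant non-major bleed, defined as any notable bleeding not classified as major". Section 6.4.1 counts physician-diagnosed stroke, DVT and PE, without requiring that the physician belong to the site.

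**The concern.** Under section 7's broad definition, bleeding, DVT, PE and stroke are all adverse events, so its sentence on questioning covers the events the trial is meant to count. It is also the only rule in the protocol on what patients may be asked. Open-ended elicitation suits unexpected events. For a pre-specified endpoint it leaves capture to what the patient chooses to mention, and in an unblinded trial (section 5.5) that may depend on what the patient expects of the drug.

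The comparison of arms is not at stake in the usual sense, because the synopsis says that the trial is not powered for it. What the pilot offers is event rates: section 1.2 hopes for a signal of benefit and safety, and section 9.1 wants a reference for later studies. Rates that are biased low would pass that error on to whoever plans the next trial.

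**Working it through.** The point rests on no planned figure, so the main check is to trace events through the rules as written.

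**1. A nosebleed or wound ooze managed at home.** It can count under section 6.3 if notable. It cannot meet section 4.1's post-discharge rule, since there is no readmission and no transfusion. No study call would find it. It reaches the EMR only if the patient raises it on a routine call, at a clinic visit or at the 30-day examination, or if the examiner elicits it by open questions.

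**2. Overlap of the readmission rule with non-major bleeding.** Section 6.3 already classes extrasurgical bleeding that leads to transfusion of two or more units of whole blood or red cells within 24-48 hours as major. For extrasurgical bleeding, the readmission rule therefore mostly selects major events. It is poorly suited to finding non-major ones.

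**3. A DVT diagnosed and treated elsewhere without admission.** It is a primary event under section 6.4.1. It may not be a serious adverse event, because section 7.1 leaves out hospital visits under 24 hours without admission unless they are life-threatening or judged an important medical event. No section provides for obtaining outside records. Blinded adjudication classifies events already found and cannot recover missed ones.

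**4. Classification.** No section says how an unrecorded event or unknown status is handled. With the EMR as the sole source, an unrecorded event would by default count as none.

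**5. Effect of one missed event.** Section 9.1 gives about 2 enrollments per month over 28 months: 2 × 28 = 56, the stated accrual, and 56 / 2 = 28 per arm, as in section 4.1. One event is 1/28 = 3.6% (exact 95% CI 0.1% to 18.3%). If it is missed, the arm shows 0/28 = 0% (0% to 12.3%).

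**6. Chance of missing a primary event.** Let p be the true event rate and m the share of events that the EMR misses. Neither is in the documents; both are assumed. The chance of at least one missed event among 56 patients is 1 − (1 − pm)^56:

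- p = 1%, m = 10%: 5%
- p = 2%, m = 25%: 24%
- p = 5%, m = 25%: 51%
- p = 5%, m = 50%: 76%

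**7. Non-major bleeding, also on assumed figures.** If 15% of patients bleed after discharge, 0.15 × 28 = 4.2 per arm. If 30% to 60% are captured, 4.2 × 0.30 = 1.3 to 4.2 × 0.60 = 2.5 are recorded.

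Items 6 and 7 show a range and are not evidence of size.

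**The case against.** A reader might infer that section 7 bars staff from asking about bleeding or stroke. The text does not go that far. It says should not, it gives a purpose, and it leaves open-ended questioning and examination available. Section 6.1 requires endpoint monitoring at the same visit, and a fair joint reading is that section 7 governs general adverse-event elicitation while section 6.1 requires specific monitoring. That answers the strong reading. It does not settle how the monitoring is done, because no section says so.

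A reader might also infer that unrecorded events are scored as event-free. No scoring rule is stated; the fault is that the rule is absent.

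Other routes of detection exist. Routine calls continue, what a patient tells the examiner can be charted in the EMR, and section 7.1.1 requires all serious events to be collected until 30 days after dosing stops, with no limit to site records. These make it less likely that an outside stroke or PE is missed. They help little with minor bleeding at home.

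It is tempting to add that apixaban events would be missed more often, since the schedule labels the clinic visits warfarin. The synopsis says the anticoagulation clinic manages both groups, so the documents do not establish a difference between arms.

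Finally, scripted questions in an open-label trial may themselves prompt answers coloured by treatment. That stands as a cost of the fix.

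**Conclusion.** The point holds as a gap in ascertainment. The larger causes are the EMR-only source and the two-unit readmission rule; the section 7 sentence adds to them by steering staff away from the direct question that could close the gap. Followed as written, the plan could under-count endpoint events to day 30, most clearly non-major bleeding and less so physician-diagnosed thromboembolism or stroke.

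The direction, biased low, follows from the rules. The size cannot be derived from the documents: the only firm figure is 3.6 percentage points per missed event in an arm of 28, and it says nothing about how likely a miss is. The change is worth making because the event rates are the pilot's main product and the remedy uses a visit that already takes place.

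**What to change.** 1. In section 7, limit the sentence on questioning to adverse events other than the protocol endpoints.
2. At the existing 30-day examination, ask every patient in both arms the same short scripted questions: any bleeding, new neurological symptoms, diagnosed clot, transfusion, or care outside the site. Chart the answers and request outside records when an answer is positive. Send possible thromboembolism or stroke to the blinded committee, and classify bleeding under section 6.3.
3. Amend section 6.1 so that outcomes come from the EMR plus this questionnaire. Amend the post-discharge bleeding rule in section 4.1 and the synopsis so that capture is no longer limited to readmissions with at least two units; otherwise the protocol would hold two conflicting rules.
4. Report patients whose endpoint status is unknown separately, rather than counting them as event-free.

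Cost: a few minutes per patient, occasional record requests, and an amendment discussed with BMS and approved by the IRB (section 10.1). No new visit or call is needed. Recorded non-major bleeding is likely to rise in both arms. Some open-label influence on prompted answers will remain; identical wording in both arms limits it but does not remove it.

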7.1 Serious Adverse Events

A **Serious Adverse Event (SAE)** is any untoward medical occurrence at any dose that:

- results in death
- is life-threatening (defined as an event in which the subject was at risk of death at the time of the event; it does not refer to an event which hypothetically might have caused death if it were more severe)
- requires inpatient hospitalization or causes prolongation of existing hospitalization (see **NOTE***: below for exceptions)

- results in persistent or significant disability/incapacity
- is a congenital anomaly/birth defect
- is an important medical event, defined as a medical event that may not be immediately life-threatening or result in death or hospitalization but, based on appropriate medical and scientific judgment, may jeopardize the subject or may require intervention (e.g., medical, surgical) to prevent one of the other serious outcomes listed above. Examples of such events include but are not limited to intensive treatment in an emergency department or at home for allergic bronchospasm; blood dyscrasias or convulsions that do not result in hospitalization.

Suspected transmission of an infectious agent (eg, pathogenic or non-pathogenic) via the study drug is an SAE.

Although pregnancy, overdose, and cancer are not always serious by regulatory definition, these events must be handled as SAEs.

***NOTE:** *The following hospitalizations are not considered SAEs:*

- A visit to the emergency room or other hospital department lasting less than 24 hours that does not result in admission (unless considered an “important medical event” or a life-threatening event)
- Elective surgery planned before signing consent
- Admissions as per protocol for a planned medical/surgical procedure
- Routine health assessment requiring admission for baseline/trending of health status (eg, routine colonoscopy)
- Medical/surgical admission other than remedying ill health state that was planned before study entry. Appropriate documentation is required in these cases
- Admission encountered for another life circumstance that carries no bearing on health status and requires no medical/surgical intervention (eg, lack of housing, economic inadequacy, caregiver respite, family circumstances, administrative reason)
-

Adverse Events of Special Interest

In this study, the following adverse events are to be reported to BMS, regardless of whether these reports are classified as serious or unexpected.

- Potential or suspected cases of liver injury including but not limited to liver test abnormalities, jaundice, hepatitis or cholestasis.

7.1.1 Serious Adverse Event Collecting and Reporting

Following the subject's written consent to participate in the study, all SAEs, whether related or not related to study drug, must be collected, including those thought to be associated with protocol-specified procedures. All SAEs must be collected that occur during the screening period and within 30 days of discontinuing dosing. If applicable, SAEs must be collected that relate to any later protocol-specific procedure (such as follow-up skin biopsy).

The investigator should report any SAE occurring after these time periods that is believed to be related to study drug or protocol-specified procedure.

An SAE report should be completed for any event where doubt exists regarding its status of seriousness.

If the investigator believes that an SAE is not related to study drug, but is potentially related to the conditions of the study (such as withdrawal of previous therapy, or a complication of a study procedure), the relationship should be specified in the narrative section of the SAE Report Form.

SAEs, whether related or unrelated to the study drug, and pregnancies must be reported to BMS within 24 hours. SAEs must be recorded on the FDA MedWatch Form 3500A ; Pregnancies on a Pregnancy Surveillance Form.

SAE Email Address: [contact]

SAE [contact]

If only limited information is initially available, follow-up reports are required. (Note: Follow-up SAE reports should include the same investigator term(s) initially reported.)

If an ongoing SAE changes in its intensity or relationship to study drug or if new information becomes available, a follow-up SAE report should be sent within 24 hours to the BMS (or designee) using the same procedure used for transmitting the initial SAE report.

All SAEs should be followed to resolution or stabilization.

7.1.2 SAE Reconciliation

The investigator will reconcile the clinical database SAE cases transmitted to BMS Global Pharmacovigilance (GPV&E). Reconciliation will occur every three months and once just prior to database lock/Final Study Report (FSR). The investigator will request a safety data reconciliation report to [contact]. BMS GPV&E will e-mail upon request from the investigator, the GPV&E reconciliation report. The data elements listed on the GPV&E safety data reconciliation report will be used for case identification purposes. If the investigator determines a case was not transmitted to BMS GPV&E, the case will be sent immediately.

7.1.3 Health Authority Reporting (US FDA IND)

Investigators must adhere to local Health Authority Reporting Requirements. For studies conducted under an investigator sponsored US FDA IND, provide details of the following:

- Any event that is both serious and unexpected must be reported to the Food and Drug Administration (FDA) as soon as possible and no later than 7 days (for a death or life-threatening event) or 15 days (for all other SAEs) after the investigator's or institution's initial receipt of the information.
- BMS will be provided with a simultaneous copy of all adverse events filed with the FDA. SAEs should be reported on MedWatch Form 3500A, which can be accessed at: <http://www.accessdata.fda.gov/scripts/medwatch/>.

MedWatch SAE forms should be sent to the FDA at:

MEDWATCH

[name]

[name]

Fax: [name] ([name])

<http://www.accessdata.fda.gov/scripts/medwatch/>

All SAEs should simultaneously be faxed or e-mailed to BMS at:

Global Pharmacovigilance & Epidemiology

Bristol-Myers Squibb Company
[contact]
Email: [contact]

7.2 Non-Serious Events

A non-serious adverse event is an AE not classified as serious.

7.2.1 Non-Serious Adverse Events (NSAEs) Collecting and Reporting

The collection of non-serious adverse event (NSAE) information should begin at initiation of study drug. Non-serious adverse event information should also be collected from the start of a placebo lead-in period or other observational period intended to establish a baseline status for the subjects.

Non-serious AEs should be followed to resolution or stabilization, or reported as SAEs if they become serious. Follow-up is also required for non-serious AEs that cause interruption or discontinuation of study drug, or those that are present at the end of study treatment as appropriate.

Non-serious Adverse Events are provided to BMS via annual safety reports (if applicable), and interim or final study reports.

7.3 Laboratory Test Abnormalities

The following laboratory abnormalities should be captured and reported as appropriate:

- Any laboratory test result that is clinically significant or meets the definition of an SAE
- Any laboratory test result abnormality that required the subject to have study drug discontinued or interrupted
- Any laboratory test result abnormality that required the subject to receive specific corrective therapy.

It is expected that wherever possible, the clinical rather than the laboratory term will be used by the reporting investigator (eg, use the term anemia rather than low hemoglobin value).

Laboratory test abnormalities are provided to BMS via annual safety reports (if applicable), and interim or final study reports.

7.4 Pregnancy

If, following initiation of the investigational product, it is subsequently discovered that a study subject is pregnant or may have been pregnant at the time of investigational product exposure, including during at least 5 half-lives after product administration, the investigational product will be permanently discontinued in an appropriate manner (eg, dose tapering if necessary for subject safety).

The investigator must immediately notify [contact] of this event via the Pregnancy Surveillance Form within 24 hours and in accordance with SAE reporting procedures.

Follow-up information regarding the course of the pregnancy, including perinatal and neonatal outcome and, where applicable, offspring information must be reported on a Pregnancy Surveillance Form.

Any pregnancy that occurs in a female partner of a male study participant should be reported to BMS. Information on this pregnancy may also be collected on the Pregnancy Surveillance Form.

Protocol-required procedures for study discontinuation and follow-up must be performed on the subject unless contraindicated by pregnancy (eg, x-ray studies). Other appropriate pregnancy follow-up procedures should be considered if indicated.

7.5 Overdose

An overdose is defined as the accidental or intentional administration of any dose of a product that is considered both excessive and medically important. All occurrences of overdose must be reported as SAEs.

7.6 Other Safety Considerations

Any significant worsening noted during interim or final physical examinations, electrocardiograms, x-rays, and any other potential safety assessments, whether or not these procedures are required by the protocol, should also be recorded as a non-serious or serious adverse event, as appropriate, and reported accordingly.

